1.0 Purpose

The purpose of this protocol is to provide continued access of the Edwards SAPIEN 3 Transcatheter Heart Valve Model 9600TFX (20, 23, 26, 29 mm) and delivery systems (transfemoral, transapical and transaortic), which are intended for use in patients with symptomatic, calcific, severe aortic stenosis for patients with intermediate risk for standard aortic valve replacement.

2.0 Device Description

The Edwards SAPIEN 3 transcatheter heart valve (THV) is comprised of a balloon-expandable, radiopaque, cobalt-chromium alloy frame, trileaflet bovine pericardial tissue valve, and polyethylene terephthalate (PET) internal fabric skirt, and a PET outer skirt. The valve is treated according to the Edwards ThermaFix process, and is packaged and terminally sterilized in glutaraldehyde.

Refer to the instructions for use for descriptions of the following SAPIEN 3 Edwards accessory devices:

- Edwards Commander Delivery System, models 9610TF23, 9610TFX23, 9610TF29 for the transfemoral procedure
- Edwards Expandable Introducer Sheath Set, models 9610ES14, 916ES23 for the transfemoral procedure
- Edwards Certitude Delivery System, models 9620TA23, 9620TA26, and 9620TA29 for transapical and transaortic procedure
- Edwards Certitude Introducer Sheath Set, models 9620IS18 and 9620IS21 for the transapical and transaortic procedure
- Ascendra Balloon Aortic Valvuloplasty Catheter model 9100BAVC for the transapical and transaortic procedure
- Crimper, model 9600CR

3.0 Background

A total of 1,078 intermediate risk patients were enrolled in the PARTNER II SAPIEN 3 intermediate (PIIS3i) cohort. Edwards has received strong feedback from the PARTNER Community that further research for both the SAPIEN 3 valve as well as the intermediate risk group is warranted to expand the device and procedural related learning as well as to address the needs of patients that are in the screening process or could present at the investigating centers.

4.0 Design

All data from Screening through 1 year; including adverse events (AE) will be entered in The Society of Thoracic Surgeons (STS) and the American College of Cardiology (ACC), TVT Registry™ (TVTR). Data excerpts of the TVTR data entered by enrolling sites will be transferred to the Sponsor on a monthly basis. All patient personal identifiers will be redacted prior to data transfer. The annual one year follow-up visit data will be entered in the TVTR, and data from years 2-5 will be obtained from the Centers for Medicare and Medicaid Services (CMS) via TVTR linkage.

Edwards or designee will monitor the patient 30-day follow up visit data.

The TVTR is a benchmarking tool developed to track patient safety and real-world outcomes related to transcatheter valve replacement, repair procedures and emerging treatments for valve disease patients. It is designed to monitor the safety and efficacy of these new technologies for the treatment of valve disease.

Patients in PIIS3i continued access must be covered by Medicare. This will enable Edwards to link to the CMS database for long term follow-up through 5 years. No other insurance provider will be accepted for enrollment.

Participating sites will maintain patient files in the same manner as they do for the initial Investigational Device Exemption (IDE) study patient populations. Refer to the PARTNER II protocol version 6.0 or most current protocol version for additional information.

5.0 Continued Access Protocol Endpoints

The primary safety and effectiveness endpoint is stroke, aortic valve reintervention and death at the 30-day follow-up visit.

Summary statistic reports for the primary safety and effectiveness endpoint will be provided at the 1 year follow-up visit.

Secondary safety endpoints will include death, annular dissection, aortic dissection, major access vascular site complication, unplanned vascular surgery or intervention, and retroperitoneal, GI and GU bleeds, and bleeding at access sites collected through the 30 day follow-up visit.

Summary statistic reports for individual rates of death and all other safety endpoints included in the TVTR data collection form in sections F, I, and on the adjudicated event rates (section J) for stroke and aortic reintervention will be provided.

6.0 Sites

Up to a total of 60 actively enrolling sites.

7.0 Enrollment

A total of 1,078 intermediate risk patients were implanted in the PIIS3i cohort. Enrollment in this continued access protocol will consist of up to a maximum of 2,000 PIIS3i patients. Patients enrolled under the PIIS3i continued access will become part of the TVTR database. Edwards will receive data excerpts from the TVTR on a monthly basis through the first year of patient registration and then yearly through follow-up year 5. Edwards will provide annual reports to the FDA based on this data through year 5 of follow up.

To ensure enrollment is representative and balanced across study sites, no site will enroll more than 15 percent of the total enrollment or implant approach.

8.0 Continued Access Study Duration

Enrollment will continue up to a maximum of 2,000 continued access patients.

Initial Enrollment: January 2015

Anticipated Enrollment Close: August 2016

9.0 Patient Population

Inclusion Criteria

All candidates for this study must meet the following criteria:

1. Patients must be covered by Medicare. This will enable Edwards to link to the CMS database for long term follow-up through 5 years. No other insurance provider will be accepted.
2. Assessment of intermediate surgical risk defined as STS 4-8% or heart team assessment of intermediate risk factors.
3. Patient has senile degenerative aortic valve stenosis with echocardiographically derived criteria: mean gradient > 40 mmHg or jet velocity greater than 4.0 m/s and an initial aortic valve area (AVA) of ≤ 0.8 cm² or indexed EOA < 0.5 cm²/m². Qualifying echo must be within 60 days of the date of the procedure.
4. Aortic valve annulus area range (273mm²-680 mm²) per 3D imaging (echo, CT, or MRI).
5. Patient is symptomatic from his/her aortic valve stenosis, as demonstrated by NYHA Functional Class II or greater.
6. The heart team agrees (and verified in the case review process) that valve implantation will likely benefit the patient.
7. Heart team agrees (a priori) on treatment strategy for concomitant coronary disease (if present).
8. The study patient or the study patient's legal representative has been informed of the nature of the study, agrees to its provisions and has provided written informed

consent as approved by the Institutional Review Board (IRB) of the respective clinical site.

9. The study patient agrees to comply with all required post-procedure follow-up visits including annual visits through 5 years and analysis close date visits, which will be conducted as a phone follow-up.

Exclusion Criteria

Candidates will be excluded from the study if any of the following conditions are present:

1. Heart team assessment of inoperability (including examining cardiac surgeon).
2. Evidence of an acute myocardial infarction \leq 1 month (30 days) before the intended treatment [(defined as: Q wave MI, or non-Q wave MI with total CK elevation of CK-MB \geq twice normal in the presence of MB elevation and/or troponin level elevation (WHO definition)].
3. Aortic valve is a congenital unicuspid or congenital bicuspid valve, or is non-calcified.
4. Mixed aortic valve disease (aortic stenosis and aortic regurgitation with predominant aortic regurgitation $>3+$).
5. Pre-existing mechanical or bioprosthetic valve in any position.
6. Complex coronary artery disease:
 - a) Unprotected left main coronary artery
 - b) Syntax score > 32 (in the absence of prior revascularization)
7. Any therapeutic invasive cardiac procedure resulting in a permanent implant that is performed within 30 days of the index procedure (unless part of planned strategy for treatment of concomitant coronary artery disease). Implantation of a permanent pacemaker or ICD is not considered exclusion criteria.
8. Any patient with a balloon valvuloplasty (BAV) $<$ 30 days of the procedure (unless BAV is a bridge to procedure after a qualifying ECHO).
9. Patients with planned concomitant surgical or transcatheter ablation for atrial fibrillation.
10. Leukopenia (WBC $<$ 3000 cell/mL), acute anemia (Hgb $<$ 9 g/dL), thrombocytopenia (Plt $<$ 50,000 cell/mL).
11. Hypertrophic cardiomyopathy with or without obstruction (HOCM).
12. Hemodynamic or respiratory instability requiring inotropic support, mechanical ventilation or mechanical heart assistance within 30 days of screening evaluation.
13. Need for emergency surgery for any reason.
14. Severe ventricular dysfunction with LVEF $<$ 20%.
15. Echocardiographic evidence of intracardiac mass, thrombus or vegetation.

16. Active upper GI bleeding within 3 months (90 days) prior to procedure.
17. A known contraindication or hypersensitivity to all anticoagulation regimens, or inability to be anticoagulated for the study procedure.
18. Native aortic annulus size < 16 mm or > 28mm as measured by echocardiogram.
19. Clinically (by neurologist) or neuroimaging confirmed stroke or transient ischemic attack (TIA) within 6 months (180 days) of the procedure.
20. Renal insufficiency (creatinine > 3.0 mg/dL) and/or renal replacement therapy at the time of screening.
21. Estimated life expectancy < 24 months (730 days) due to carcinomas, chronic liver disease, chronic renal disease or chronic end stage pulmonary disease.
22. Expectation that patient will not improve despite treatment of aortic stenosis.
23. Significant aortic disease, including marked tortuosity (hyperacute bend), aortic arch atheroma [especially if thick (> 5 mm), protruding or ulcerated] or narrowing (especially with calcification and surface irregularities) of the abdominal or thoracic aorta, severe “unfolding” and tortuosity of the thoracic aorta. (Transfemoral)
24. Iliofemoral vessel characteristics that would preclude safe placement of 14F or 16F introducer sheath such as severe obstructive calcification, severe tortuosity or minimum average vessel size less than 5.5 mm. (Transfemoral).
25. Currently participating in an investigational drug or another device study. Note: Trials requiring extended follow-up for products that were investigational, but have since become commercially available, are not considered investigational trials.
26. Active bacterial endocarditis within 6 months (180 days) of procedure.
27. Evidence of intracardiac mass, thrombus, vegetation, active infection or endocarditis.
28. Inability to tolerate anticoagulation/antiplatelet therapy.
29. For transfemoral approach only: Femoro-iliac vessels < 5.5 mm for the 23 mm and the 26 mm system and < 6.0 mm for the 29 mm system.

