10.1.0 Screening Assessments

Screening assessments should be completed within 30 days of patient enrollment unless otherwise specified.

- Medical history
- STS Risk Score
- NYHA classification
- Syntax Score (conducted in the absence of prior revascularization)
- Hemoglobin, Platelet Count, Creatinine
- Transthoracic (TTE) or transesophageal echocardiogram (TEE)
- Cardiac Imaging (ECHO, CTA, or cardiac MRI) with 3D reconstruction of the aortic root to determine aortic valve annulus area must be completed within 180 days of patient enrollment.
- Reference S3 Sizing Guide (Protocol 6.0, Appendix U) for sizing recommendations
- Thoracic x-ray, an abdominal angiogram, and CT angiograms or MRI, and with complete visualization of both iliacs and femorals to the aorta. In the situation where patients have compromised renal function that precludes the use of contrast agents, MR imaging may be used as an alternative. CT scans are strongly recommended, particularly in patients with femoral arteries less than 7 mm; (must be within 180 days of patient enrollment). Patients with previously documented inadequate femoral access [(Iliofemoral vessel characteristics that would preclude safe placement of 22F or 24F introducer sheath (14F or 16F for S3) such as severe obstructive calcification, severe tortuosity or minimum average vessel size less than 6 mm (20, 23 and 26 mm THV minimum vessel size \geq 5.5 mm / 29 mm THV minimum vessel size \geq 6.0 mm for S3)] don't require repeat testing.
- Left and right cardiac catheterization to assess the severity of aortic stenosis and severity of coronary artery disease if applicable (< 90 days before procedure)

Data must be entered in the STS/ACC TVT Registry. Data in the TVTR data forms will be included in monthly data transfers from the TVTR to the Sponsor. All patient personal identifiers will be redacted prior to data transfer.

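### Do the 3D annulus area range (273–680 mm²) and the echo annulus exclusion (below 16 or above 28 mm) contradict each other?

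*Protocol*

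**What the plan says.** Protocol section 9.0 limits annulus size in two places. Inclusion criterion 4 gives an area: "Aortic valve annulus area range (273mm²-680 mm²) per 3D imaging (echo, CT, or MRI"). Exclusion criterion 18 gives a linear size: "Native aortic annulus size < 16 mm or > 28mm as measured by echocardiogram".

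The same section says how the lists combine. The inclusion list opens with "All candidates for this study must meet the following criteria", the exclusion list with "Candidates will be excluded from the study if any of the following conditions are present".

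Section 10.1.0 lists two separate screening items. One is "Cardiac Imaging (ECHO, CTA, or cardiac MRI) with 3D reconstruction of the aortic root to determine aortic valve annulus area". The other is the echocardiogram itself, "Transthoracic (TTE) or transesophageal echocardiogram (TEE"). The protocol gives no conversion between area and diameter and does not name the echo view or axis for criterion 18. Section 10.2 has the case review board assess eligibility before enrollment, and under section 12.0 the sponsor checks eligibility violations in the monthly extracts and at source verification.

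**The concern.** Both criteria bound the size of the same structure, so a reader naturally puts them on one scale. On the circle formula they match at neither end. At the top, the diameter limit is tighter than the area limit, so part of the range that criterion 4 admits appears to be taken back by criterion 18. At the bottom, the 16 mm limit is looser than the area limit and seems to do nothing. Echo is also one of the modalities accepted for the 3D area, so a single examination might pass criterion 4 and fail criterion 18.

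If this were a true contradiction, up to 60 sites (section 6.0) could select patients with large annuli differently, and the check in section 12.0 could classify the same patient in two ways.

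**Working it through.** **Inputs.** From section 9.0: area 273 to 680 mm² (criterion 4) and linear size 16 to 28 mm (criterion 18). The annulus shape is not in the protocol. It is an assumption, taken here as an ellipse with axis ratio r = minor/major; r = 1 is a circle. The protocol states no derived figure to reproduce.

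**Step 1: circle.** With A = πd²/4 and d = √(4A/π):

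- 16 mm gives π × 16²/4 = 201.1 mm²; 28 mm gives π × 28²/4 = 615.8 mm².
- 273 mm² gives √(4 × 273/π) = 18.64 mm; 680 mm² gives √(4 × 680/π) = 29.42 mm.
- Apparent band at the top: 680 − 615.8 = 64.2 mm². As a share of the area range: 64.2/(680 − 273) = 64.2/407 = 15.8%.

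The conversions behind the concern are therefore right for a circle.

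**Step 2: ellipse.** The area at which the minor axis reaches 28 mm is 615.8/r. The area at which the major axis reaches 28 mm is 615.8 × r.

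| r | Area where minor axis = 28 mm | Area where major axis = 28 mm |
|---|---|---|
| 1.00 | 616 mm² | 616 mm² |
| 0.95 | 648 mm² | 585 mm² |
| 0.90 | 684 mm² | 554 mm² |
| 0.85 | 724 mm² | 523 mm² |
| 0.80 | 770 mm² | 493 mm² |

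On the minor axis the band closes when 615.8/r reaches 680, that is at r = 615.8/680 = 0.906. At or below that ratio even a 680 mm² annulus measures no more than 28 mm. On the major axis the band widens instead. At the lower end, the 16 mm limit comes into play for a 273 mm² annulus on the minor axis once r is below 201.1/273 = 0.736, so it is not redundant for every shape.

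The 616–680 mm² band is thus one point in a span that runs from no band at all to one starting below 500 mm². The protocol does not fix where in that span it lies.

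**Step 3: how the criteria combine.** On these two criteria alone:

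| 3D area within 273–680 mm² | Echo size within 16–28 mm | Result |
|---|---|---|
| yes | yes | passes both |
| yes | no | excluded by criterion 18 |
| no | yes | fails criterion 4 |
| no | no | fails both |

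Each row has one result. A candidate with an area of 650 mm² and an echo size above 28 mm is excluded; one with the same area and an echo size of 28 mm or less is not. No ranking of the two measurements is needed, because both must be satisfied. The eligibility check in section 12.0 gives the same answer for the same pair of values.

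**The case for a change.** The strongest reply is that criterion 18 says only size, and that the choice of echo measurement changes the answer. For any ellipse above 616 mm², the area-derived diameter is the geometric mean of the two axes and exceeds 28 mm; the arithmetic mean of the axes and the major axis exceed it too. Only a reading near the minor axis can fall at or below 28 mm. A single 3D echo showing 650 mm² has an area-derived diameter of √(4 × 650/π) = 28.8 mm, and there a difference between echo and CT explains nothing. If the exclusion was meant to narrow the range, the 680 mm² ceiling cannot be reached on most readings.

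The geometry is correct, and it stands that the protocol names neither the view nor the axis. Two sites could in principle measure the same annulus differently. That, however, is variation in how a measurement is taken, which a fuller definition would reduce. It does not make the two criteria contradictory. An exclusion that trims part of an inclusion range is the normal working of such lists, and a limit that rarely acts is not an error. The case review board assesses each candidate before enrollment, although section 10.2 does not say how it handles annulus measurements. Section 10.1.0 refers to a sizing guide in Protocol 6.0, Appendix U, which is not at hand, so whether it defines the measurement cannot be judged.

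**Conclusion.** The concern does not hold. The protocol uses two different measurements, says that both lists bind, and so gives one answer for each pair of values. The conversion to 616 mm² is correct for a circle, but the 64 mm² band rests on two assumptions that the protocol does not make: a circular annulus, and an echo size equal to the area-derived diameter. With a shorter-axis reading and an axis ratio of about 0.906 or less, the band is zero; with a longer-axis reading it is wider than 64 mm². The protocol therefore does not show that the limits are inconsistent rather than specific to each modality.

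The 15.8% is a share of square millimetres, not of patients, and the number of patients in any such band cannot be derived. No effect is shown on the endpoints in section 5.0. The unnamed echo view or axis is a missing detail. This conclusion takes no view on which annulus limits are clinically right.

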10.2 Case Review Process

Patients must meet the fundamental enrollment criteria of severe, symptomatic, calcific aortic stenosis. Upon meeting these eligibility criteria, the site investigators (per site heart team assessment) shall then determine the patient's risk for operative morbidity and mortality. Patients determined to be operable must have a STS score of 4 - 8% or a defensible

intermediate risk profile determined by the heart team and approved by the case review board process.

The PARTNER II trial operations include a case review process prior to enrollment of patients. After screening assessments are made, the patient's qualifying criteria are reviewed by the case review board where the members will assess patient eligibility and access approach. Upon approval, the patient may be enrolled into the study. The case approval decision will be documented by the Sponsor.

The study procedure should occur within two weeks (14 days) of case approval.

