12.0 Protocol Deviations

The sponsor will check inclusion/exclusion for violations during the monthly extract receipt from the TVTR as well as during source document verification monitoring.

Table 1.0 - Schedule of Events

							1 yr Follow-Up
							30 D Follow-Up
							Discharge
							Post Procedure
							During procedure
							Pre-Procedure
							Screening
Non-Invasive Tests							
TTE or TEE	X			X			X
Fluoroscopic imaging implanted valve			X				
Pulmonary Functions (optional)							
Radiation Dosage			X				
12 Lead ECG				X			
Invasive Tests							
Cardiac Imaging	X						
CT Thoracic/Abdomen (or MRI) with visualization of iliac and femoral arteries	X						
Cardiac Catheterization	X						
Supra-aortic angiogram or TEE				X			
Hemodynamics (see section 9.4 of protocol 6.0 or most current protocol version)					X

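### Exclusion 10 states its white-cell and platelet limits per mL, which is 3 and 50 cells per microlitre and does not fit the leukopenia and thrombocytopenia it names; check the unit on the source page and, if it is mL, reconcile

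*Protocol*

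**What the plan says.** Protocol section 9.0 introduces the exclusion list with "Candidates will be excluded from the study if any of the following conditions are present", so each item is an operative bar to enrolment. Exclusion 10 has three limbs: "Leukopenia (WBC $<$ 3000 cell/mL), acute anemia (Hgb $<$ 9 g/dL), thrombocytopenia (Plt $<$ 50,000 cell/mL". The white-cell and platelet limbs are per mL and the haemoglobin limb is per dL. The only other exclusion that prints a laboratory number with a concentration unit is Exclusion 20: "Renal insufficiency (creatinine > 3.0 mg/dL) and/or renal replacement therapy at the time of screening".

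Eligibility is policed at two points. Section 10.2 sends each patient through a case review board before entry: "Upon approval, the patient may be enrolled into the study". Section 12.0 adds a later check: "The sponsor will check inclusion/exclusion for violations during the monthly extract receipt from the TVTR as well as during source document verification monitoring".

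For matters not covered, section 4.0 points elsewhere: "Refer to the PARTNER II protocol version 6.0 or most current protocol version for additional information". That parent protocol is not at hand.

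**The concern.** The two cell-count limits and the conditions they are meant to define do not agree. A limit of 3 white cells or 50 platelets per microlitre describes a near-absence of cells. That is not what leukopenia or thrombocytopenia ordinarily means, so number, unit and label conflict within one line.

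What is at stake is whether the exclusion does any work. It is a safety criterion in a protocol that may enrol up to 2,000 patients at up to 60 sites. If a site or the sponsor's eligibility check applies number and unit as written, patients with the named conditions would pass. Trial estimates are not at stake: no endpoint, sample size or analysis uses these limits.

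**Working it through.** The protocol gives no derived figure to reproduce. The check is a unit conversion, followed by a search of the rest of the document for anything that corrects the unit.

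**Inputs (Protocol section 9.0, Exclusion 10)**
- White cells: "Leukopenia (WBC $<$ 3000 cell/mL"
- Platelets: "thrombocytopenia (Plt $<$ 50,000 cell/mL"
- Conversion: 1 mL = 1,000 microlitres

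**Step 1. Convert as written.** Limit per microlitre = limit per mL / 1,000.
- White cells: 3000 / 1,000 = 3 per microlitre (3 × 10^6 per litre).
- Platelets: 50,000 / 1,000 = 50 per microlitre (5 × 10^7 per litre).

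**Step 2. Size the gap.** The same numerals read per microlitre would be 3 × 10^9 and 50 × 10^9 per litre.
- White cells: 3000 / 3 = 1,000.
- Platelets: 50,000 / 50 = 1,000.

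This shows only how much the unit matters. It does not say which limit is right.

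**Step 3. Compare with the labels.** The protocol gives no reference range, so the comparison rests on the ordinary meaning of the two words. A thousandfold gap does not depend on where a given laboratory sets its normal limits.

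**Step 4. Look for a correction elsewhere.**
- Section 10.1.0 lists haemoglobin, platelet count and creatinine at screening, without units and without a white-cell count.
- Section 10.3 lists no blood counts.
- Section 10.0 describes these lists as an overview and defers to the registry data collection form, which is not at hand.
- No section shown restates the limits. Whether the parent protocol does is unknown.

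**Step 5. Scope.** Four laboratory limits in the exclusion list carry a number and a concentration unit: white cells, haemoglobin and platelets in Exclusion 10, and creatinine in Exclusion 20. Two are per mL and two per dL, and only the two per mL are in question. That is 2 of the 3 limbs of 1 of 29 exclusion criteria.

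**The case against.** The strongest objection is that the fault may lie in the copy and not in the plan. Everything turns on one character, and a program reading a PDF can turn a micro sign into an m. Comparison signs around this line appear in several forms in the available text, so symbols there were not copied uniformly. No micro sign appears anywhere else, so the reading of that symbol cannot be tested. That the unit appears twice is little help, since both occurrences would probably be misread alike. The per-dL limits contain no micro sign and are no evidence either way. This objection stands as a limit: the available text cannot settle which case applies. It is a reason to look at the source page first, not to assume that the page is right.

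The second objection concerns the consequence. The section 12.0 check can miss a violation only if the count reaches the extract or the source documents and is compared with a literal per-mL limit. A white-cell count is not among the listed screening or pre-procedure tests, and no unit is given for the recorded platelet count. This narrows what can be said about that check, particularly for white cells, but does not remove the mismatch in the criterion.

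The third objection is that no experienced clinician would apply 3 white cells per microlitre, that the conditions are named in words, and that the case review board sees each patient's qualifying criteria before enrolment. This also stands, and it is why the point is minor.

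**Conclusion.** The concern holds as a minor point, with medium confidence. As the text reads, both cell-count limits in Exclusion 10 are a factor of 1,000 below the same figures per microlitre, do not match the conditions they define, and taken literally would exclude practically nobody with those conditions.

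This rests on two assumptions: that the source page prints mL, and that leukopenia and thrombocytopenia carry their ordinary meaning. If the page prints microlitre, the factor is 1 and the point lapses. Nothing here shows that any patient was wrongly enrolled, and the expected practical effect is small.

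**What to change.** Check the unit in Exclusion 10 against the source page. If it is printed as mL, reconcile number, unit and named condition for the white-cell and platelet limbs, and use the reconciled limits in the eligibility checks under section 12.0. Which limits are right is for the sponsor and the investigators to decide.

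The cost is one look at the page and, if needed, a one-line correction. No new procedure, visit or data item is required.
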